### Secondary Outcomes:

Secondary endpoints including 12-item walking scale and urodynamic studies (binary,  $\geq 20\%$  improvement in bladder capacity vs  $< 20\%$ ) will also be analyzed. Linear regression models for continuous outcomes and logistic regression models for discrete outcomes will be used to assess the independent effect of treatment status on secondary outcomes, controlling for co-variates.

- MSFC → T25FW (time in seconds) + 9HPT (time in seconds) + PASAT (time in seconds)
  - MSFC score =  $\{Z_{\text{arm, average}} + Z_{\text{leg, average}} + Z_{\text{cognitive}}\} / 3.0$
  - reduction in score indicates improvement
- EDSS
  - ranges from 3 to 6.5 for our study (scale ranges from 0 to 10). No units.
  - reduction in score indicates improvement
- T25FW (timed 25-foot walk)
  - time in seconds
  - reduction in time indicates improvement
- 9HPT (9-hole peg test)
  - time in seconds
  - reduction in time indicates improvement
- 12-item MS Walking Scale
  - Total score out of 60, and %
  - reduction in scores or % means improvement
- Urodynamic studies
  - PVR
  - Cystometry with simultaneous measurements of bladder, urethral and subtracted rectal pressures for first sensation
  - Maximum bladder capacity
  - Urethral pressure profile with functional length measurement maximum closing pressure
  - Bladder pressure was assessed with filling and sphincter relaxation and synergic voiding assessed

**Study Name:** Autologous, Bone Marrow-Derived Mesenchymal Stem Cell-Derived Neural Progenitor Cells, Expanded Ex Vivo; Administered Intrathecally (Phase II Trial)

**Principal Investigator:** [name]

- Urinary peak flow rate was also measured.
- 6-Minute Walk Test
  - Distance in meters
  - Increase in distance indicates improvement

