6.4 Schedule of activities (Study Table)

| Tests and Assessments | Pre-treatment Phase | | | Treatment Phase, year 1 ² | | Safety FU | Outcome assessments I ³ | Treatment Phase, year 2 ² | | Safety FU | Outcome assessments II ² | Final FU ³ |
|--|--|-------------------------------|----------------------------|---|---|---|------------------------------------|---|---|--|-------------------------------------|------------------------------------|
| | Screening Visit Month -4 (Within 4 months prior to treatment phase) | Bone marrow visit Month -3 | Baseline visit Month -1 | Treatment group Months 0, 2, 4, 6, 8, 10 | Placebo group Months 0, 2, 4, 6, 8, 10 | FU by phone 48 hrs and 1 week after each treatment or placebo | All groups Month 13 | Treatment group (crossover from placebo) Months 14, 16, 18, 20, 22, 24 | Placebo group (crossover from treatment) Months 14, 16, 18, 20, 22, 24 | Follow-up by phone 48 hrs and 1 week after each treatment or placebo | All groups Month 27 | End of study follow-up Month 36 |
| ICF | X | | | | | | | | | | | |
| Serum and Plasma Biomarker Analysis Blood draw | | | | X | X | | | X | X | | | X |
| Screening Blood Draw ⁴ | X | | | | | | | | | | | |
| Bone marrow aspiration | | X | | | | | | | | | | |
| LP Procedure | | | | X | X | | | X | X | | | X |
| CSF aspiration for biomarker analysis | | | | X | X | | | X | X | | | X |
| Vital signs | X | X | X ⁵ | X | X | | X | X | X | | X | X |
| Physical exam | X | | X ⁵ | | | | X | | | | X | X |
| Neurol. exam | X | | X ⁵ | | | | X | | | | X | X |
| Headache pain scale | | X | | | X (12 total) | X | | | X (12 total) | X | X | |
| EDSS | X | | X ⁵ | X ⁶ | X ⁶ | | X | X' | X' | | X | X |
| MSFC (T25FW, 9HPT, PASAT) | | | X | X ⁶ | X ⁶ | | X | X ⁷ | X ⁷ | | X | X |
| 6 Minute Walk Test (6MW) | | | X | | | | X | | | | X | X |
| UD | | | X | | | | X | | | | X | |
| Brain, Cervical, and Thoracic MRI ±Gd | | | X | | | | X | | | | X | X |
| Twelve Item MS Walking Scale | | | X | | | | X | | | | X | X |
| Infectious disease test | X | | | | | | | | | | | |
| Pregnancy test (females) | X | | | | | | | | | | | |
| Drug & Nicotine Urine Testing | X ⁵ | | | | | | | | | | | |
| Urinalysis & Culture | | | X | | | | X | | | | X | |
| Bladder Survey | | | X | | | | X | | | | X | |
| Infectious Disease Questionnaire | X | | | | | | | | | | | |

¹Screening Blood Draw will include CBC with differential, ESR, Comprehensive Metabolic Panel, PT/PTT, and Thyroid Function Tests

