## SAP Revision History

Version #	Version date	Reason for Revision
Version 1	Started Nov 2019 – Issued Dec 2020	Objective of SAP: To describe planned analysis of study objectives prior to data analysis (anticipated initial data analysis to be performed December 2021).
Version 2	July 2021	Finalize SAP for submission to FDA: update personnel list, update study design to indicate parallel group design, more detailed description of statistical analysis added.

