- Patients with active thyroid disease resulting in hyperthyroidism or hypothyroidism (Only well controlled patients with labs in the normal range will be included) because of hormone influence on cell growth
- History of central nervous system infection or immunodeficiency syndromes due to increased risk of CNS infection
- Preexisting blood disease (such as bone marrow hypoplasia, leukopenia, thrombocytopenia, or significant anemia) due to invasive nature of bone-marrow aspiration
- Previous or current history of a coagulation disorder
- Any metal in the body, which is contraindicated for MRI studies
- Allergy to any of the antibiotics used in this study, e.g. tobramycin, vancomycin, or gentamicin
- Allergy to, or have had adverse reactions to gadolinium or other contrast agents to be used in the study
- Patients with alcohol or other substance abuse problems that may affect stem cell growth; habitual drug (including marijuana and nicotine) abusers, will be excluded from the study
- Other major disease that, in the opinion of the Principal Investigator, would preclude participation in the study
- Patients with HBV, HCV, syphilis, HIV-1, or HIV-2.
- Any evidence of significant cognitive dysfunction based on a screening history and physical examination because it would preclude giving a truly informed consent
- Patients who are enrolled in another clinical trial for MS treatment or who have received any study drug/biologics within the last 6 months. Additionally, while in

**Study Name:** Autologous, Bone Marrow-Derived Mesenchymal Stem Cell-Derived Neural Progenitor Cells, Expanded Ex Vivo; Administered Intrathecally (Phase II Trial)

**Principal Investigator:** [name]

the trial, patients may not enroll in any other clinical trial for MS or any other condition.

- Patients who are anticipated to have difficulty accessing the intrathecal space related to scoliosis, obesity, or any other relevant factors determined by the PI.

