## 1.5 Sample Size and Randomization

A total of 50 study subjects will be enrolled based on power analysis based on 20 participants in each group of the Phase II study. Group sample size of 20 in the treatment group and 20 in the placebo group achieve more than 80% power to detect a difference between the group proportions of 35%, using a two-sided Z-test with pooled variance and using a significance level of 0.05. This calculation assumes that 40% of patients in the treatment group and 5% of patients in the placebo group achieve at least one of the EDSS-Plus components. The prevalence of patients with improved outcome is informed by the results of our Phase I trial, in which 40% of patients experienced a decrease of 0.5 or more on EDSS. A total of 50 patients (25 patients in each group) will initially be enrolled to account for an expected attrition rate of 20%.

Subjects will be stratified according to baseline EDSS score (3.0-4.0, 4.5-5.5, 6.0, and 6.5) and disease subtype (SPMS or PPMS), and block randomized within each stratum. The total number of subjects to be enrolled in each subgroup is shown below. Subjects are stratified and block randomized into placebo or treatment group in order of date of enrollment based on randomization scheme designated by [name]. Study subjects are randomized in an equal fashion to study treatment and placebo at initial randomization.

EDSS	SPMS	PPMS
3.0-4.0	10	4
4.5-5.5	10	2
6.0	10	2
6.5	10	2
Total # of patients:	40	10

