### **4 STATISTICAL ANALYSIS OF THE PRIMARY AND SECONDARY STUDY OBJECTIVES**

#### **4.1 Analysis of the Primary Study Objective**

##### Primary Outcome:

The primary analysis will include all subjects meeting inclusion and exclusion criteria and who have completed a year of treatment/placebo and the 3 month post-treatment assessment. EDSS Plus composite score from 3 month post-treatment assessment will be compared to baseline.

Descriptive statistics will be calculated for patients at baseline for the entire cohort as well as by treatment status. Treatment and placebo group patients will be compared on continuous and discrete baseline characteristics to assess randomization.

The EDSS-Plus scale will be used as our primary endpoint with improvement on one or more of the 3 components (EDSS, T25FW and 9HPT). Improvement is defined as  $\geq 1$  point decrease from baseline EDSS if EDSS at entry is  $\leq 5.5$ , and a  $\geq 0.5$  point decrease from baseline EDSS if EDSS at entry is  $\geq 6.0$ ,  $\geq 20\%$  positive change in T25FW, and/or  $\geq 20\%$  positive change in 9HPT confirmed. The primary endpoint of improvement on one or more of the 3 EDSS-Plus categories between treatment and placebo groups will be assessed bi-varately using the chi-square or Fisher's exact test, as appropriate, at year 1, 2, and 3 of the study. Adjusted odds ratio (95%CI) between treatment and placebo groups at each time point will be estimated through mixed effect logistic regression with fixed effect of time, treatment, relevant covariates, and random effect of patients. The three components of the EDSS-Plus composite score will also be assessed individually at all time points. A longitudinal linear mixed-effect model will be used to assess longitudinal change (percentage change in mean time) from baseline to 3 years for T25FW and 9HPT, with random intercepts for patients and taking into account treatment status (treatment vs placebo), disease subtype (SPMS vs PPMS) and time-progression status interaction.

**Study Name:** Autologous, Bone Marrow-Derived Mesenchymal Stem Cell-Derived Neural Progenitor Cells, Expanded Ex Vivo; Administered Intrathecally (Phase II Trial)

**Principal Investigator:** [name]

Under parallel design, we will compare the outcomes of interest between the two study treatments, with outcomes at 1 year as the primary time point, secondary analyses will evaluate outcomes at years 2 and 3.

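### Does the SAP's MSFC rule (three timed inputs, equal plus signs, lower is better) conflict with itself?

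*SAP*

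**What the plan says.** The MSFC is one of nine secondary outcomes in SAP 1.3.2, and Protocol 9.1.2 gives the same list. The scoring rule stands only in SAP 4.1, Secondary Outcomes. The inputs are T25FW in seconds, then "9HPT (time in seconds) + PASAT (time in seconds"). The score is the sum of an arm, a leg and a cognitive Z score divided by 3.0. The line directly below gives the direction: "reduction in score indicates improvement".

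The same list gives T25FW and 9HPT their own entries, each in seconds with less time better. It states an upward direction where one applies, for the 6-Minute Walk Test: "Increase in distance indicates improvement". PASAT has no entry of its own.

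The protocol adds nothing on scoring. Its schedule of activities (6.4) names the parts, "MSFC (T25FW, 9HPT, PASAT"), and section 11.1 lists the MSFC among the case report form contents. Neither document gives a reference mean or SD for the Z scores.

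For the primary analysis the SAP also says: "The three components of the EDSS-Plus composite score will also be assessed individually at all time points". Those components are EDSS, T25FW and 9HPT.

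**The concern.** Equal plus signs are safe only if all three inputs point the same way. If PASAT were recorded as a number of correct answers, a higher value would be better and the printed unit would be wrong. One of two things would then happen.

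- If the walking and peg times enter untransformed, the cognitive term opposes them and a real benefit is diluted.
- If all three are aligned so that higher is better, the score is sound, but the printed direction would label benefit as worsening.

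T25FW and 9HPT are analysed separately, so an error in either would show. No separate PASAT analysis is planned, so a reversed cognitive term could pass unseen. The absence of a reference mean and SD adds to the impression of an unfinished rule.

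**Working it through.** The plan states no MSFC effect, variance or power, so there is no planned figure to reproduce. The check is sign arithmetic on the SAP formula, MSFC = (Z_arm + Z_leg + Z_cog)/3.

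**1. Printed units (PASAT as a time).** Better means a smaller value on every component.
- 1 SD better on all three: (-1-1-1)/3 = -1.00.
- 1 SD better on cognition only: (0+0-1)/3 = -0.33.

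Both are reductions, and the SAP calls a reduction an improvement. There is no conflict.

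**2. Assumption: PASAT as a count, with times left raw.** The documents do not state this.
- 1 SD better on all three: (-1-1+1)/3 = -0.33.
- 0.4 SD better on arm and leg, 1 SD better on cognition: (-0.4-0.4+1)/3 = +0.07, read as worsening although every part improved.

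**3. Assumption: PASAT as a count, with times reversed to match.** 1 SD better on all three gives (1+1+1)/3 = +1.00. Reversing the sign of a whole score leaves a two-sided p-value unchanged, so only the direction label would need turning round.

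**4. Size under step 2.** Further assumptions, none from the documents: 0.5 SD benefit on arm and on leg, PASAT benefit p, unit component SDs, correlation r = 0.3 in the direction of benefit, and a two-sided t-test at 0.05. The 20 per arm comes from SAP 1.5 ("Group sample size of 20 in the treatment group and 20 in the placebo group"), where it was set for the binary primary endpoint.
- Aligned shift = (1.0 + p)/3; unaligned shift = (1.0 - p)/3.
- Aligned SD = sqrt(3 + 6r)/3 = sqrt(4.8)/3 = 0.730.
- Unaligned SD = sqrt(3 - 2r)/3 = sqrt(2.4)/3 = 0.516.

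| PASAT benefit p (SD) | Shift, unaligned / aligned | Power, unaligned / aligned |
|---|---|---|
| 0 | 0.33 / 0.33 | 51% / 29% |
| 0.25 | 0.25 / 0.42 | 32% / 42% |
| 0.5 | 0.17 / 0.50 | 17% / 56% |
| 1.0 | 0 / 0.67 | 5% / 80% |

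The two scores have equal power at p = (k-1)/(k+1) with k = sqrt(4.8/2.4) = 1.414, so p = 0.414/2.414 = 0.17 SD. At r = 0 the scores tie at p = 0 (43% each), and the aligned score leads at 0.25 SD (60% against 27%). At r = 0.5 the unaligned score is still ahead at 0.25 SD (37% against 35%). The result therefore runs from a gain to a loss, depending on values that nobody has stated.

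**5. The missing reference values.** With Z_j = (x_j - m_j)/s_j and one reference for all patients at a visit, every m_j is the same constant in both arms. The between-arm difference is the sum over components of Δ_j/(3 s_j), where Δ_j is the arm difference in component j. The reference mean drops out. The reference SDs set only the relative weight of each component.

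**The case for a change.** The strongest case for a change needs no assumption about PASAT. A Z score cannot be computed without a mean and an SD, and the SAP gives neither. MSFC is measured at baseline and at months 6, 13, 20, 27 and 36, so a pooled baseline, a per-visit or an external reference could each be chosen, and two programmers could produce different scores from the same data. Settling this after unblinding would mean choosing with results in view, and the SAP revision history puts the first analysis close at hand ("anticipated initial data analysis to be performed December 2021"). A few lines would close the gap.

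The omission is real, and that part stands. It carries less weight than it seems to. As step 5 shows, the reference mean cannot move the treatment comparison at a visit, and the SDs affect only component weights. The sign of each term is not a free choice either: the SAP fixes the direction of the composite and of both timed tests, and the recorded PASAT field will show which kind of score it holds. Anyone computing the MSFC must look at that field.

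The PASAT part does not stand as a finding. Its only ground for doubting the printed unit lies outside the documents. Even if a count is granted, a PASAT effect near zero is plausible, because the trial excludes patients with "Any evidence of significant cognitive dysfunction based on a screening history and physical examination". At zero effect the unaligned score loses no shift and, at the assumed correlation of 0.3, has the higher power.

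**Conclusion.** No change to the plan follows. The MSFC text in SAP 4.1 agrees with itself on its own units, and the alleged contradiction appears only if PASAT is not a time, which neither document shows. If it were a count, the effect would range from higher power, through an unchanged p-value with a reversed label, to a substantial loss. That range is set entirely by assumed effects and correlations.

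What the documents do show is missing detail: no reference mean or SD, no explicit sign per component and no PASAT scoring line. This is working detail that analysts supply when they build the score. It bears on one of nine secondary endpoints. The primary EDSS-Plus comparison uses EDSS, T25FW and 9HPT, so neither it nor the sample size depends on PASAT or the MSFC, and the two timed MSFC components are analysed separately in any case. Neither document ties a decision or a formal claim to the MSFC result.

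The conclusion rests on reading the SAP's stated unit as written. A count in the recorded data would be visible when the score is computed, and aligning it would be a routine scoring step.

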### Exploratory Outcomes:

Individual MRI measures obtained from NeuroQuant software will be analyzed as an exploratory outcome. Brain, cervical and thoracic spine MRI scans will be obtained at baseline, and at months 13, 27, and 36. Assessments will include the following:

- Proton density and T2-weighted two-dimensional (2D) multislice turbo/fast spin-echo
- T1-weighted three-dimensional (3D) spoiled gradient recalled echo both pre-contrast and after a 10 minute delay following injection of gadolinium post-contrast sequencing
- 2D T2 weighted Fluid -Attenuated Inversion Recovery (FLAIR)
- MTR MR tractography dependent on the number of tracts followed
- DTI – A T2 SPC 3D Flair sagittal sequence, EP diffusion, and a gradient filed mapping

Using the CorTechs NeuroQuant software package a multi-structure atrophy report will be generated for all brain MRI scans as well as a Lesion Quant Flair assessment of total number and volume of lesions; the total number and volume of enlarging lesions and the total number and volume of new lesions. All lesions to be counted would have to be at least 3 voxels in size. For lesions to be considered enhancing an increase in intensity by at least 20% on the post-contrast images compared to the baseline T1 sequence lesions. The total number of new or enlarging T2 hyperintense lesions as detected by MRI will be assessed by a negative binomial model. Percentage change in total brain volume from baseline to month 13 will be assessed using an MMRM analysis.

CSF biomarker analysis will also be included as an exploratory outcome. CSF, plasma, and serum samples will be obtained at the time of each treatment, and 3 months following the 12th treatment, for a total of 13 samples of each type.

## 4.2 Analysis of the Secondary Study Objective

### Safety Analysis

All observed or volunteered adverse events (serious or non-serious) and abnormal test findings, regardless of study group or suspected causal relationship to the study drug(s) will be recorded in the subjects' case histories and submitted for yearly reporting to the DSMB and FDA. For safety analysis, the following will be tabulated:

- Incidence of Adverse Events
- Relationship pf Adverse Events to Investigational Product

**Study Name:** Autologous, Bone Marrow-Derived Mesenchymal Stem Cell-Derived Neural Progenitor Cells, Expanded Ex Vivo; Administered Intrathecally (Phase II Trial)

**Principal Investigator:** [name]

- Severity of Adverse Event
- Serious Adverse Events
- Adverse Events Leading to Treatment Discontinuation
- Death
- Adverse Events of Special Interest

Summary descriptive statistics will be reported for each adverse event. For continuous outcome, mean(sd)/median(IQR) for whole sample and each group will be reported along with p-values from two-sample two-sided t-test or Wilcoxon rank-sum test as appropriate. For binary outcomes, number (%) of events will be reported along with p-values from Chi-squared test or Fisher's exact test as appropriate. Linear or logistic regression will be applied to estimate the treatment effect on each safety outcome. Analyses will be performed at the end of each of the three years.

All analyses will be performed in SAS Version 9.4 (SAS Institute Inc., Cary, NC) or R version 4.0.3 (2020-10-10).

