**TISCHMS-MSCNP-002
CLINICAL STUDY PROTOCOL**

NCT03355365

CLINICAL PROTOCOL: Summary Information

| | |
|--|--|
| TITLE | Autologous, Bone Marrow-Derived Mesenchymal Stem Cell-Derived Neural Progenitor Cells (MSC-NP), Expanded Ex Vivo; Administered Intrathecally |
| SPONSOR | Tisch MS Research Center of New York (Tisch MSRCNY) [name] [contact] |
| PROTOCOL NUMBER | TISCHMS-MSCNP-002 |
| VERSION NUMBER AND DATE | V8 08/26/2021 |
| PHASE OF CLINICAL INVESTIGATION | Phase II |
| IND NUMBER | 13889 |
| PRINCIPAL INVESTIGATOR | [name], FAAN Director and Chief Research Scientist Tisch MS Research Center of New York |
| NUMBER OF SITES | 1 |
| STUDY DESIGN | Phase 2, Double-Blind, Placebo-Controlled, randomized, Parallel Study of Intrathecal autologous MSC-NP Cells in Patients With MS |
| PRIMARY OBJECTIVE | To determine efficacy of multiple (6) intrathecal administrations of autologous MSC-NPs compared to placebo through assessment of disability outcomes |
| SECONDARY OBJECTIVES | To determine continued safety and tolerability of multiple intrathecal injections of MSC-NPs in patients with MS |
| NUMBER OF SUBJECTS | 50 |
| SUBJECT SELECTION CRITERIA | Inclusion Criteria (summary): SPMS or PPMS patients who have significant disability (EDSS between 3.0 and 6.5) that was not acquired within the last 12 months. Exclusion Criteria (summary): EDSS > 6.5, or anyone with comorbidities (past or present) that would put them at a higher risk for safety complications. |
| INVESTIGATIONAL NEW DRUG / INTENDED USE | Bone Marrow-Derived Mesenchymal Stem Cell-Neural Progenitor Cells (MSC-NP) for use as treatment for multiple sclerosis |
| CONTROL GROUP OR OTHER STUDY ARMS (if applicable) | Placebo (LP procedure) |
| DURATION OF SUBJECT | Subjects will participate in the study for 3 years |

| | |
|--|---|
| PARTICIPATION AND DURATION OF STUDY | 
 • Pretreatment screening and bone marrow aspiration: potentially up to 4 months • Treatment phase: 2 years, total 12 treatments (6 MSC-NP injections, 6 placebo lumbar punctures) every 2 months • Follow-up: 1 year |
| PRIMARY ENDPOINT | EDSS Plus (measured at baseline, month 6, month 13, month 20, month 27, and month 36) |

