Based on these pre-clinical and early clinical data supporting safety and efficacy, we are conducting an FDA-approved Phase I clinical trial to test safety and tolerability of 3 separate doses of up to 10 million MSC-NPs administered intrathecally with doses spaced 3 months apart [4]. Twenty subjects with progressive MS were enrolled. Inclusion criteria included those with established disability (EDSS 3.5 to 8.0) and stable disability (no progression 6-12 months prior to enrollment). All 20 patients received the 3 MSC-NP treatments spaced 3 months apart with 3 month follow-up assessments. The dosing regimen was found to be well tolerated, with only minor adverse events including transient headache (lasting only up to 48 hours post-treatment) and less commonly a transient fever (less than 100°F; always over within 24 hours). There were no safety concerns associated with the treatment. Efficacy trends show that 15 of the 20 patients have improved in at least one of the following categories: ≥ 0.5 improvement in EDSS; at least 20% improvement in 25 feet timed walk, greater than 20% positive change in none hole PEG test, moderate to marked improvement in muscle strength, or symptomatic and/or urodynamic improvement in bladder function. These results are remarkable because such reversal of disability in long standing SPMS and PPMS has not previously been reported.

Based on our phase I trial results that establish safety and tolerability and suggest efficacy, we have designed a phase II study with the primary goal of establishing efficacy. We propose to use the intrathecal (IT) route of injection of administration. This is because the IT route in our phase I study has proved safe, tolerable and given positive results and it has not been established that these

cells given by other routes such as IV is effective. In our clinical studies to date, doses of up to 10 million MSC-NPs are well tolerated [3, 4], therefore we propose to continue the same dosage for this phase II study.

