### 1.2 Study Design

The study is a Phase II, double-blind, placebo-controlled, randomized, parallel group design with a compassionate crossover element. The IT-MSC-NP treatments and all clinical assessments take place at a single center (Tisch MSRCNY). Both the patient and the examining neurologist are blinded to the treatment. The treating clinician ([name], principal investigator) and the cell manufacturing coordinator ([name], co-PI) are not blinded. The total study duration is 3 years upon enrollment. Each subject will initially attend 1 screening visit, 1 visit for bone marrow extraction, and 1 baseline visit. In the first year, each subject will receive 6 intrathecal injections of MSC-NPs or placebo spaced 2 months apart, followed by an outcome assessment visit 3 months after the 6th treatment. In the second year, subjects will cross-over into the opposite group, and will receive 6 intrathecal injections of placebo or MSC-NPs spaced 2 months apart, followed by an outcome assessment visit 3 months after the 12th treatment. There is an additional follow-up visit at the end of year 3.

**Study Name:** Autologous, Bone Marrow-Derived Mesenchymal Stem Cell-Derived Neural Progenitor Cells, Expanded Ex Vivo; Administered Intrathecally (Phase II Trial)

**Principal Investigator:** [name]

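### The safety analysis does not define its unit or how years 2 and 3 are grouped, and it gives up the within-subject comparison of cell and placebo procedures for acute reactions

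*SAP*

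**What the plan says.** For continuous safety outcomes, SAP 4.2 (Safety Analysis) reports "p-values from two-sample two-sided t-test or Wilcoxon rank-sum test as appropriate". For the rest: "For binary outcomes, number (%) of events will be reported along with p-values from Chi-squared test", or from Fisher's exact test. It adds: "Linear or logistic regression will be applied to estimate the treatment effect on each safety outcome". On timing: "Analyses will be performed at the end of each of the three years".

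The section names no paired test, subject effect, clustering or period term. It does not say whether an event count is of subjects or of procedures, whether the later analyses are cumulative or by year, or whether subjects are grouped by randomised arm or by procedure received. For the primary outcome, by contrast, SAP 4.1 specifies a logistic model with a random patient effect.

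The Protocol summary table gives "total 12 treatments (6 MSC-NP injections, 6 placebo lumbar punctures) every 2 months", and SAP 1.2 states: "In the second year, subjects will cross-over into the opposite group, and will receive 6 intrathecal injections of placebo or MSC-NPs". Headache is scored by phone after every procedure. Protocol 6.2 and 6.3 list calls at 48 hours, 1 week and 1 month; the table in 6.4 lists only the first two. Both include the 48-hour call. Protocol 1.2 describes the Phase I reactions as "transient headache (lasting only up to 48 hours post-treatment" and, less often, a fever that was over within 24 hours.

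**The concern.** Safety and tolerability is the secondary objective in both documents. Headache is the reaction that the protocol expects from the cells (Protocol 5.1). People differ in how readily they get a headache after lumbar puncture, and a comparison within the same person removes that difference. The crossover supplies this comparison for every completer, but no method in SAP 4.2 uses it.

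The open choices also matter. The unit of counting and the grouping of years 2 and 3 can change both the estimate and its error rate. If they are settled after the data are seen, the safety result depends on that choice.

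**Working it through.** **Plan's own figure.** The documents state no power, margin or precision for safety. Their only power figure is for efficacy (SAP 1.5: 20 per group, 40% against 5%, more than 80%). Exact enumeration of the pooled Z-test gives 82.0%, so it reproduces. It has no bearing on safety.

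**Inputs.** From the documents: six procedures per subject per year, one type in year 1 and the other in year 2; N = 20 completers per arm. Assumed, because the documents give no value: within-subject correlation ρ of 0.1 to 0.4 between procedures; a headache rate where one is needed; no carry-over; no variation between subjects in the treatment effect. σ² is the variance of one procedure's outcome.

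**Precision.**
- Year 1, two-sample on subject means: 2σ²(1+5ρ)/(6N).
- Within-subject difference over 12 procedures, 2N subjects: 2σ²(1−ρ)/6 ÷ 2N = σ²(1−ρ)/(6N). With equal arms, adjusting for period leaves this unchanged.
- Variance ratio: 2(1+5ρ)/(1−ρ). Its square root is the ratio of interval widths. The leading 2 comes from adding year-2 data; the rest comes from pairing.

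**Type I error if procedures are treated as independent.**
- Within year 1, the true variance is 1+5ρ times the assumed one, so the rate is P(|Z| > 1.96/√(1+5ρ)).
- Over both years by procedure received, ignoring pairing, the true variance is 1−ρ times the assumed one, so the rate is P(|Z| > 1.96/√(1−ρ)).

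| ρ | Variance ratio | Width ratio | Variance ratio without the factor 2 | Type I, year 1, procedures as independent | Type I, both years, unpaired |
|---|---|---|---|---|---|
| 0.1 | 2×1.5/0.9 = 3.3 | 1.8 | 1.7 | 11% | 3.9% |
| 0.2 | 2×2.0/0.8 = 5.0 | 2.2 | 2.5 | 17% | 2.8% |
| 0.4 | 2×3.0/0.6 = 10.0 | 3.2 | 5.0 | 26% | 1.1% |

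**Absolute size, one example.** Assume a 20% headache rate (σ² = 0.2×0.8 = 0.16), ρ = 0.2, N = 20. The year-1 standard error is √(0.16×2×2.0/120) = 0.073, a 95% half-width of 14.3 percentage points. The within-subject standard error is √(0.16×0.8/120) = 0.033, a half-width of 6.4 points.

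**Simulation checks.**
- Subject-level year-1 tests kept false positives between about 3% and 7%, apart from 8.7% in one sparse setting with an uncorrected chi-squared test.
- Procedure-level chi-squared in year 1 gave 10% to 11% at ρ = 0.1. Pooled over both years without pairing it gave 3.5% to 4.2%.
- With 20 per arm, headache after 20% and 35% of procedures and ρ about 0.13, power was 20% (any headache, Fisher), 49% (t-test on subject means) and 97% (paired, 12 procedures). These rates are illustrative.

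**Grouping after year 2.** Let c and p be the expected events per cell and per placebo procedure. Cumulatively, one arm has 6c + 6p and the other 6p + 6c. Apart from period effects the difference is zero whatever c − p is.

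**The case against.** The study is described as parallel-group with a compassionate crossover. In year 1 each subject receives one procedure type, so a subject-level comparison by randomised arm is valid and keeps the protection of randomisation. That stands: the cost there is precision, not error.

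A reader might infer that the safety tests will produce too many false positives. The documents do not support that. It happens only if procedures within one year are counted as independent observations. SAP 4.2 does not say so, and its listing of adverse event incidence is ordinarily a count of subjects. Pooling both years by procedure received without pairing errs in the conservative direction.

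A reader might also infer that year-2 safety data are discarded. They are not: analyses are planned after each year. This is why the factor of 2 is separated out above.

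Protocol 9.4 describes safety as assessed through summaries, and SAP 4.2 names no headache test, so headache falls under its general rules. Power for headache is not a planned quantity; interval width is the more relevant measure.

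Absence of carry-over is not established either. It rests on symptom duration in 20 Phase I subjects, and Protocol 1.2 reports cell engraftment in mice 8 weeks after the third injection. For a headache lasting up to 48 hours with procedures 2 months apart it is a plausible assumption, but it should be stated as one.

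**Conclusion.** The point holds as one of undefined analysis and lost precision. SAP 4.2 leaves the unit of analysis and the grouping of years 2 and 3 open, and names no method that uses the six-and-six structure, although SAP 4.1 already uses a patient effect for efficacy. For acute reactions the valid year-1 test gives intervals 1.8 to 3.2 times wider than a within-subject analysis at ρ from 0.1 to 0.4. Pairing alone, without the extra year, accounts for a variance factor of 1.7 to 5. These sizes rest on the assumed correlation, no carry-over, and a treatment effect that does not vary between subjects. If later analyses were cumulative by randomised arm, the cell-versus-placebo contrast would disappear; the SAP should rule that out. The primary efficacy analysis is not affected. This is a cheap improvement.

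**What to change.** In SAP 4.2:

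1. State the unit for every safety table. Keep the year-1 subject-level tables by randomised arm, and subject-level tables for serious and later-onset events.
2. For headache, fever and other events with onset within 48 hours of a procedure, add a mixed or GEE model with the procedure as the record: logistic for events, linear for the pain score. Use procedure type received, period and procedure number as fixed effects and subject as the cluster, over all 12 procedures. Report the cell-versus-placebo effect with its 95% CI.
3. State that this model assumes no carry-over for acute reactions, with the reason. The year-1 table serves as the comparison that does not need the assumption.
4. Group year-2 events by procedure received, and say whether the year-2 and year-3 reports are by year or cumulative.

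The cost is SAP wording and one more model, with no new data or visits. The downside is reliance on the carry-over assumption.
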